4.1.1 Screening (Day -35 to Day 0)

The following procedures must be performed and recorded at the Screening visit:

1. Review study procedures and information regarding the study including the potential risk and benefits of SB204 with the subject and obtain written informed consent/assent.
2. Obtain demographic information.
3. Obtain subject's medical history and medication history.
4. Verify appropriate contraception being used for WOCBP per Section 6.4.
5. Collect blood pressure and pulse rate after the subject has been sitting quietly for 5 minutes.
6. Perform a brief physical examination.
7. Obtain pregnancy test (WOCBP only) and evaluate results. If pregnancy test is positive, the subject may not participate in the study.
8. Perform Investigator's Global Assessment (IGA).
9. Perform lesion counts. Inflammatory and non-inflammatory lesion counts will be performed on the entire face.
10. Confirm subject meets eligibility criteria.
11. Review prohibited medications, acne treatments, and supplements that should not be used prior to Baseline and during the trial.
12. Collect AEs related to study procedures performed since signing of informed consent.
13. Confirm the study schedule with the subject.

4.1.2 Baseline (Day 0)

The following procedures must be performed and recorded at the Baseline visit:

1. Update medication history and record concomitant medication information.
2. Perform a brief physical examination. If the Baseline visit occurs within 7 calendar days of the Screening visit, the physical examination does not need to be repeated.
3. Obtain pregnancy test (WOCBP only) and evaluate results. If pregnancy test is positive, the subject may not participate in the study. If the Baseline visit occurs within 7 calendar days of the Screening visit, the pregnancy test does not need to be repeated.
4. Collect blood pressure and pulse rate after the subject has been sitting quietly for 5 minutes.
5. Perform cutaneous tolerability assessment.
6. Perform IGA.
7. Perform lesion counts.

8. Have subject wash face and dry with lint free towel in preparation for photographs (if applicable).
9. Collect photographs (if applicable).
10. Confirm eligibility and randomize subject.
11. Dispense subject diary and study drug. Instruct subject on dispensing, mixing, and application of study product and diary completion.
12. Update AE information for AEs reported at Screening and record any new AEs (e.g., AEs related to washout, AEs related to study procedures performed at visit, etc.).
13. Confirm the study schedule with the subject.

4.1.3 Week 2 (Day 14)

The following procedures must be performed and recorded at the Week 2 visit:

1. Update concomitant medication information.
2. Update AE information and record any new AEs if applicable.
3. Collect blood pressure and pulse rate after the subject has been sitting quietly for 5 minutes.
4. Perform cutaneous tolerability evaluation.
5. Perform IGA.
6. Perform lesion counts.
7. Review diary completion and study drug compliance with subject.
8. Review and confirm the study schedule with the subject.

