1.5 SUMMARY OF BENEFITS AND RISKS

The pathogenesis of acne vulgaris includes several mechanisms which are potential targets for nitric oxide. Nitric oxide has been demonstrated in vitro to decrease *P. acnes*, inhibit several inflammatory pathways relevant in acne, and to decrease sebum production. In two completed Phase 2 studies, subjects with acne treated with SB204 had lower inflammatory and non-inflammatory lesion counts with greater 'success' on the dichotomized IGA score ('clear/almost clear' and at least a two grade change from Baseline) at the end of treatment when compared to subjects treated with Vehicle Gel. Once daily dosing was as effective as twice daily dosing. In the studies conducted to date, the systemic AE profile was similar between subjects treated with SB204 and subjects treated with Vehicle Gel. SB204 4% has been generally well tolerated and was not associated with a safety or tolerability signal.

In the maximum use pharmacokinetic study, there was no observed hMAP3 in plasma and no change in nitrate levels after topical application of SB204 8% twice daily to approximately 17% body surface area (BSA).

A transient (approximately 5-10 minutes), asymptomatic erythema has been observed in some subjects shortly after application of SB204 which is a physiologic response (vasodilation) to local nitric oxide release. In the most recently completed study, local application-site reactions were reported in approximately 5% of subjects treated with SB204. These local application-site reactions resolved after discontinuation of the product and by the end of the study. Topical application has been generally well-tolerated as assessed by scores for erythema, peeling, pruritus, and burning/stinging. Tolerability will be assessed during the planned study, and discontinuation criteria for intolerance by individual subjects is described in Section 6.7.

Both SB204 and Vehicle Gel contain alcohol; inadvertent administration to the eyes may result in ocular irritation and should be avoided. Should the product be accidentally instilled in the eye(s), prompt flushing with copious amount of normal saline or water is recommended.

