3.1.2 Tolerability Endpoints

The cutaneous tolerability assessments include the evaluator's assessment of erythema, scaling, dryness, and the subject's report of pruritus and burning/stinging based on the preceding 24 hours.

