4.1.5 Week 12/ET (Day 84)

The following procedures must be performed and recorded at the Week 12/ET visit:

1. Update concomitant medication information.
2. Perform a brief physical exam.
3. Update AE information and record any new AEs.
4. Obtain UPT (WOCBP only) and evaluate results.
5. Collect blood pressure and pulse rate after the subject has been sitting quietly for 5 minutes.
6. Perform cutaneous tolerability evaluation.
7. Perform IGA.
8. Perform lesion counts.
9. Have subject wash face and dry with lint free towel in preparation for photographs (if applicable).
10. Collect photographs (if applicable).
11. Collect returned study drug and diary, perform accountability, and review diary completion and study drug compliance with subject.

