4.2.1 Investigator Global Assessment

The Investigator's Global Assessment Score will be a static assessment that is independent of the Baseline score. The evaluator will make the assessment without referring to the Baseline value and prior to performing lesion counts. The assessment should be made approximately three feet from the subject. The same evaluator should perform each study assessment for each study subject whenever possible, for consistency in evaluations.

Subjects are eligible to participate in the study if they have a Baseline IGA score of 3 (moderate) or 4 (severe).

The following scores will be used to assign IGA scores:

Grade	Description
0	Clear: Clear skin with no inflammatory or non-inflammatory lesions.
1	Almost clear: Rare non-inflammatory lesions with rare papules (papules may be resolving and hyperpigmented, though not pink-red).
2	Mild: Some non-inflammatory lesions with no more than a few inflammatory lesions.
3	Moderate: Up to many non-inflammatory lesions and may have some inflammatory lesions, but no more than one nodulocystic lesion.
4	Severe: Up to many non-inflammatory and inflammatory lesions, but no more than a few nodulocystic lesions

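### On-treatment visit lists put tolerability scoring directly before IGA and lesion counts, by the same evaluator role; Table 1 shows the reverse order and no text says which governs

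*Protocol*

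**What the plan says.** Each visit has a numbered list; the Week 2 list opens with "The following procedures must be performed and recorded at the Week 2 visit". From Week 2 onward, "Perform cutaneous tolerability evaluation" is the item directly before IGA, and lesion counts follow IGA. The AE item comes earlier still: "Update AE information and record any new AEs if applicable" is item 2 at Weeks 2, 4 and 8, and "Update AE information and record any new AEs" is item 3 at Week 12/ET.

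Tolerability covers the evaluator's view of erythema, scaling and dryness, and the subject's "report of pruritus and burning/stinging based on the preceding 24 hours" (Section 3.1.2). Section 4.3 has the evaluator assess the face at Baseline and every study visit. Section 4.2 asks that the same blinded evaluator do IGA and lesion counts throughout.

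The only order rule for efficacy ratings is in Section 4.2.1: "The evaluator will make the assessment without referring to the Baseline value and prior to performing lesion counts". The synopsis repeats the part about IGA preceding counts. Neither places tolerability or AE questions relative to IGA.

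Table 1 lists IGA, lesion counts, tolerability and, last, AEs. Section 4.1 names the procedures required before randomization in that same relative order.

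**The concern.** IGA success and lesion counts are judged by a person, and all three outcomes must succeed for efficacy to be shown (Section 7.4.1). The protocol treats order as a bias control when it puts IGA ahead of the counts and away from the Baseline value. It gives no such rule for the step most likely to yield clues about treatment. SB204 releases nitric oxide, and Section 1.5 reports transient erythema in some SB204 subjects and says "local application-site reactions were reported in approximately 5% of subjects treated with SB204". A site that works down the lists would have the rater score redness and hear about stinging, then rate IGA and count lesions straight away.

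If that shifted the ratings of recognised subjects, it would do so in one arm more than the other. The planned IGA difference is small (7% against 13%, Section 7.8), so even a modest shift would be visible against it. The direction is unknown.

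**Working it through.** **1. Order in the lists (item numbers, Sections 4.1.1 to 4.1.5)**

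| Visit | AEs | Tolerability | IGA | Lesion counts |
|---|---|---|---|---|
| Screening | 12 | none | 8 | 9 |
| Baseline | 12 | 5 | 6 | 7 |
| Week 2 | 2 | 4 | 5 | 6 |
| Weeks 4 and 8 | 2 | 5 | 6 | 7 |
| Week 12/ET | 3 | 6 | 7 | 8 |

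The order in question holds at all four on-treatment visits. It does not hold at Screening, where "Collect AEs related to study procedures performed since signing of informed consent" follows the counts and tolerability is not scored. At Baseline it holds for tolerability only, and no drug has yet been applied.

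**2. Who does what.** Tolerability (Sections 3.1.2 and 4.3) and IGA with lesion counts (Section 4.2) belong to the evaluator. Nothing separates the two tasks between people. AE assessment belongs to the Investigator (Section 6.2), who is not said to be the evaluator.

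**3. Is the numbering binding?** No sentence says so. Section 4.1 requires the AE assessment before randomization, yet the Baseline list has randomization at item 10 and AEs at item 12, so that list cannot be a strict sequence. Table 1 runs the other way but is not declared a sequence either. The order of tolerability and IGA is therefore unsettled.

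**4. How strong could the clue be?** Section 1.5 puts the erythema at about 5 to 10 minutes, and Section 3.4 has the gel applied before bedtime, so the flush should normally be gone by the visit. The 24-hour recall of itching and burning/stinging does reach back to the previous evening's application. The 5% reaction figure has no vehicle counterpart.

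**5. Illustration, for IGA alone.** The plan gives no figure for this effect.

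Inputs from the protocol: 650 per arm, 7% vehicle success, planned difference 6 points (Section 7.8), 5% reactions on SB204 (Section 1.5). Assumptions not in the protocol: all of that 5% are recognised, no vehicle subject is, and their chance of IGA success rises by s = 10, 20 or 30 points.

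- Bias b = 0.05 × s
- SE = √[(0.07 × 0.93 + (0.07 + b)(0.93 − b)) / 650]
- With no true effect, P(significant in favour of SB204) = P(Z > 1.96 − b/SE)

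| s | b (points) | b / 6 points | SE | P |
|---|---|---|---|---|
| 0 | 0 | 0% | – | 2.5% |
| 10 | 0.5 | 8% | 0.0144 | 5.3% |
| 20 | 1.0 | 17% | 0.0146 | 10.1% |
| 30 | 1.5 | 25% | 0.0148 | 17.1% |

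If a share v of vehicle subjects were recognised as SB204 with the same shift, the bias would be (0.05 − v) × s, which is zero at v = 5%. If the shift were downward, a recognised subject's chance cannot fall below zero. At the planned 13%, and with recognised subjects otherwise average, the loss is at most 0.05 × 13 = 0.65 points.

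**The case against.** The strongest reply is that the lists are checklists. They say what must be done, the Baseline list cannot be followed literally, and Table 1 shows IGA and counts first. Where the sponsor cares about order, it says so in words. This stands against any claim that the protocol mandates tolerability before IGA. It does not supply a rule: if order is free, the ratings are unprotected, and the numbered lists are the most detailed visit instructions a site has.

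The second reply is that the clue is weak. The erythema is brief and asymptomatic, and Section 1.5 reports no tolerability signal at 4%. Section 1.4 describes similar AE profiles on active and vehicle, and both gels contain alcohol. Without a vehicle rate, a reaction does not identify treatment. All of this stands, and it is why the bias is only possible.

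The third is that reordering removes little. Redness and scaling remain visible during IGA, and by Week 12 the same evaluator will normally have scored tolerability at Weeks 2, 4 and 8. This also stands; only the elicitation at the same visit is removed.

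A reader might go further and infer that the rater is exposed at every visit, or that AE answers reach the rater by design. The first fails at Screening, and at Baseline no treatment clue can exist. The second fails because AE questions are the Investigator's task, although nothing prevents one person from holding both roles.

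**Conclusion.** The point holds in a limited form. At Weeks 2, 4, 8 and 12/ET the lists put tolerability scoring directly before the co-primary ratings, by the same evaluator role. Table 1 and Section 4.1 point the other way, and no text resolves it.

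The illustrated 0.5 to 1.5 points rests on an assumed rating shift, full recognition of the 5% and none on vehicle. It also attributes the whole effect to visit order. A reader might take the 5.3% to 17.1% as the trial's false-positive risk; it is not. It concerns IGA alone, and a spurious IGA result cannot demonstrate efficacy without both lesion-count outcomes. The case for change rests on its negligible cost, not on evidence of bias. Because this is a rule for site conduct, an SAP could not supply it.

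**What to change.** In Section 4.2, state that at each post-Baseline visit IGA, then lesion counts, are completed and recorded before the evaluator performs the tolerability evaluation or hears any AE responses. Renumber Sections 4.1.3 to 4.1.5 so that these procedures follow the order in Table 1. Screening and Baseline need no change for this purpose.

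The cost is a text edit and a line in site training, with no added procedure, staff or visit. The safeguard is partial, since visible signs and memory of earlier tolerability scores remain. Giving tolerability and AE questions to another staff member, where a site can do so, would also remove the carry-over of scores, but calls for a second person.

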4.1.4 Weeks 4 and 8 (Days 28 and 56)

The following procedures must be performed and recorded at the Week 4 and Week 8 visits:

1. Update concomitant medication information.
2. Update AE information and record any new AEs if applicable.
3. Obtain UPT (WOCBP only) and evaluate results.
4. Collect blood pressure and pulse rate after the subject has been sitting quietly for 5 minutes.
5. Perform cutaneous tolerability evaluation.
6. Perform IGA.
7. Perform lesion counts.

8. Have subject wash face and dry with lint free towel in preparation for photographs (if applicable).
9. Collect photographs (if applicable).
10. Collect returned study drug and diary, perform accountability, and review diary completion and study drug compliance with subject.
11. Dispense new study drug and diary.
12. Review and confirm the study schedule with the subject.

4.1.5 Week 12/ET (Day 84)

The following procedures must be performed and recorded at the Week 12/ET visit:

1. Update concomitant medication information.
2. Perform a brief physical exam.
3. Update AE information and record any new AEs.
4. Obtain UPT (WOCBP only) and evaluate results.
5. Collect blood pressure and pulse rate after the subject has been sitting quietly for 5 minutes.
6. Perform cutaneous tolerability evaluation.
7. Perform IGA.
8. Perform lesion counts.
9. Have subject wash face and dry with lint free towel in preparation for photographs (if applicable).
10. Collect photographs (if applicable).
11. Collect returned study drug and diary, perform accountability, and review diary completion and study drug compliance with subject.

4.1.6 Discontinuation/Withdrawal Procedures

A subject may voluntarily withdraw from study participation at any time. If the subject withdraws consent and discontinues from the study, the Investigator will attempt to determine the reason for discontinuation and record the reason in the subject's study records and in the study database. If a subject is withdrawn because of an AE, that AE should be indicated as the reason for withdrawal. In the event of early discontinuation, (i.e., prior to Week 12/Day 84 visit) and whenever possible, the subject should be asked to return to the study center to complete the Week 12/ET evaluations. Subjects who withdraw from the study will not be replaced.

If at any time during the study the Investigator determines that it is not in the best interest of the subject to continue, the subject will be discontinued from participation. The Investigator can discontinue a subject at any time if medically necessary. The Investigator may discontinue a subject's participation if the subject has failed to follow study procedures or to keep follow-up appointments. Appropriate documentation in the subject's study record and the study database regarding the reason for discontinuation must be completed.

All subjects who fail to return to the study center for the Week 12/ET visit will be contacted by telephone to determine the reason(s) why the subject failed to return for the necessary visit or elected to discontinue from the study. If a subject is unreachable by telephone after a minimum of two documented attempts (one attempt on two different days), a certified letter will be sent requesting that the subject contact the Investigator.

Reasons for an Investigator's withdrawal of a subject may include, but are not limited to, the following:

- Safety (e.g., severe adverse reactions, pregnancy);
- Lack of efficacy as determined by the Investigator;
- When the requirements of the protocol are not respected (e.g., significant issues with dosing compliance);
- When a concomitant medication or treatment likely to interfere with the results of the study is reported, or required, by the subject (the Investigator will decide, in consultation with Chiltern whether the subject is to be withdrawn);
- When a subject is lost to follow-up. The Investigator will try twice to reach the subject by telephone and will send a certified follow-up letter before considering that the subject is lost-to-follow-up. These actions will be reported on the subject's study record and a copy of the follow-up letter maintained in the Investigator's file.

Refer to Section 6.7 for a discussion of criteria for discontinuation of individual subjects from the study.

All premature discontinuations and their causes must be carefully documented by the Investigator on the subject's study record and in the study database. In no case will a subject who has been assigned a study number and randomized into the study be replaced by another using the same randomization number or treatment assignment.

All Week 12/ET evaluations should be performed at the time of premature discontinuation. All data gathered on the subject prior to termination will be made available to Chiltern.

Study completion or reason(s) for discontinuation as listed in the study record will be entered into the study database as follows:

- Completed
- Adverse Event
- Lack of Efficacy as determined by the Investigator
- Withdrawal by Subject
- Physician Decision
- Protocol Violation
- Lost to Follow-Up
- Pregnancy
- Worsening of Condition
- Other

Novan has the right to terminate or stop the study at any time. Should this be necessary, the Investigator will ensure that proper study discontinuation procedures are completed.

4.2 EFFICACY ASSESSMENTS

The same blinded evaluator should perform Investigator Global Assessments and lesion counts at Screening, Baseline and Weeks 2, 4, 8, and 12/ET. In the event that this is not possible due to unforeseen circumstances, a different blinded evaluator may evaluate the subject. However, the same evaluator should evaluate subjects at the Baseline and Week 12 (or early termination) evaluations.

4.2.1 Investigator Global Assessment

The Investigator's Global Assessment Score will be a static assessment that is independent of the Baseline score. The evaluator will make the assessment without referring to the Baseline value and prior to performing lesion counts. The assessment should be made approximately three feet from the subject. The same evaluator should perform each study assessment for each study subject whenever possible, for consistency in evaluations.

Subjects are eligible to participate in the study if they have a Baseline IGA score of 3 (moderate) or 4 (severe).

The following scores will be used to assign IGA scores:

Grade	Description
0	Clear: Clear skin with no inflammatory or non-inflammatory lesions.
1	Almost clear: Rare non-inflammatory lesions with rare papules (papules may be resolving and hyperpigmented, though not pink-red).
2	Mild: Some non-inflammatory lesions with no more than a few inflammatory lesions.
3	Moderate: Up to many non-inflammatory lesions and may have some inflammatory lesions, but no more than one nodulocystic lesion.
4	Severe: Up to many non-inflammatory and inflammatory lesions, but no more than a few nodulocystic lesions

4.2.2 Lesion Counts

The facial area lesion counts will be taken from the forehead, right and left cheeks, chin and nose. The lesion count groups will be inflammatory and non-inflammatory. Facial inflammatory lesions (pustules, papules, nodules and cysts) will be counted and recorded. Non-inflammatory lesions (open and closed comedones) will be counted and recorded. The following are definitions of each lesion type:

Inflammatory lesions are defined as follows:

Papule - A small, superficial, circumscribed, palpable lesion elevated above the skin surface, less than 10 mm in diameter

Pustule - A superficial elevated lesion that contains yellow fluid (pus) within or beneath the epidermis

Nodule - A firm (indurated) lesion greater than 10 mm in diameter and that is thicker or deeper than the average papule

Cyst - Spherical swelling that contains fluid or semisolid material

Non-inflammatory lesions are defined as follows:

Open comedones (blackhead) - Plugged follicular units with brown/black central debris

Closed comedones (whitehead) - Plugged follicular units with white central debris

4.3 TOLERABILITY ASSESSMENTS

The evaluator will assess the subject's face at Baseline and each study visit. The cutaneous tolerability assessment for visits other than Baseline should be performed at least 30 minutes after study drug application. Cutaneous tolerability evaluations will include erythema, scaling, dryness, pruritus and burning/stinging. Pruritus and burning/stinging will be based on the subject's report for the previous 24 hours. Cutaneous tolerability endpoints will be reported as an AE if they reach severe and/or result in subject's discontinuation from the study. Subjects who develop intolerance to the product as defined by scores of 3 (severe) on two or more categories of tolerability

(erythema, scaling, dryness, pruritus, burning/stinging) shall be discontinued from the study. Cutaneous tolerability assessments will be performed according to the following scales:

Erythema

Score	Description
0-None	No evidence of erythema present
1-Mild	Slight pink coloration
2-Moderate	Definite redness
3-Severe	Marked erythema, bright red to dusky dark red in color

Scaling

Score	Description
0-None	No scaling
1-Mild	Fine scales present to limited areas of the face, barely perceptible
2-Moderate	Fine scale generalized to all areas of the face
3-Severe	Scaling and peeling of skin over all areas of the face

Dryness

Score	Description
0-None	No dryness
1-Mild	Slight but definite roughness
2-Moderate	Moderate roughness
3-Severe	Marked roughness

Pruritus

Score	Description
0-None	No itching
1-Mild	Slight itching, not very bothersome
2-Moderate	Moderate amount of itching, somewhat bothersome
3-Severe	Severe amount of itching, definite discomfort and sleep may be disturbed

Burning/Stinging

Score	Description
0-None	No burning/stinging
1-Mild	Slight warm, burning/stinging sensation; not very bothersome
2-Moderate	Definite warm, burning/stinging sensation that is somewhat bothersome
3-Severe	Hot, tingling/sensation that has caused definite discomfort and may have disturbed sleep

